- ^s Tumor assessment (CT or MRI of chest, abdomen, and pelvis, plus other sites of known disease at baseline) will be performed every 6 weeks for the first 8 cycles, and then every 12 weeks thereafter. Imaging should be completed within a window of -3 days prior to D1 of odd cycles and should be reviewed before study drug administration on D1 for dosing determination. Patients who discontinue treatment for reasons other than PD will undergo tumor assessment in accordance with the original schedule relative to C1D1. Tumor assessment/imaging must be performed at the time of treatment discontinuation, unless it has been done within the past 4 weeks. If disease progression according to RECIST (version 1.1) is documented at any time, no further tumor/response assessment will be required.
- ^t May be performed any time within 28 days prior to C1D1 and includes assessments completed at the clinical site as part of standard of care, and prior to the signing of the informed consent, if the assessments were performed in compliance with the protocol requirements. Baseline assessment must include CT or MRI imaging of the chest and abdomen, through the level of the adrenals, and brain, if clinically indicated, as well as other sites of known disease.
- ^u From the 30-Day Safety Follow-up visit, follow-up for OS, PFS, and first subsequent anti-cancer therapy, if available, will be obtained every 3 months (\pm 14 days) until 2 years after the first dose of study drug, death, loss to follow-up, withdrawal of consent, or end of the whole trial. Follow-up information about overall survival may be obtained by phone.
- ^v Archival tissue sample is mandatory for patients in Part B who have archival tissue available; a tissue block is preferred. In the event that a tissue block is unavailable, 12-20 formalin-fixed paraffin-embedded unstained slides may be submitted. If there is not enough archival tumor tissue, a new tumor tissue biopsy sample must be obtained during screening, prior to starting study treatment. (See Section [5.7.1](#)).

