3.3. Discontinuation from Study Treatment

Patients will be discontinued from study treatment for any of the following reasons:

- Disease progression (patients who are receiving clinical benefit in the opinion of the treating Investigator may be allowed to stay on study after consultation with the Medical Monitor).
- Intolerable toxicity or abnormal laboratory values thought to be related to drug toxicity.
- Conditions requiring therapeutic intervention not permitted by the protocol.
- Intercurrent illness that may interfere with the patient's ongoing participation in the study (this will be at the Investigator's discretion).
- Inability of the patient to comply with study requirements.
- Patient lost to follow-up.
- Patient requests to discontinue treatment.
- Patient withdraws consent from study participation altogether.
- Pregnancy.
- Study termination.

After discontinuation from protocol treatment, patients must be followed for AEs for 30 days after their last dose of study drug. All new AEs occurring during this period must be reported and followed until resolution unless, in the opinion of the Investigator, these values are not likely to improve because of the underlying disease. In this case, the Investigator must record his or her reasoning for this decision in the patient's medical records and indicate on the AE pages of the electronic case report form (eCRF) that the outcome is not resolved.

All patients who have Grade 3 or 4 laboratory abnormalities (per NCI [CTCAE Version 5.0](#)) at the time of discontinuation must be followed until the laboratory values have returned to Grade 1 or 2 unless it is, in the opinion of the Investigator, not likely that these values are to improve. In this case, the Investigator must record his or her reasoning for making this decision in the patient's medical records and indicate on the AE pages on the eCRF that the outcome is not resolved.

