4.5.2. Prohibited Concomitant Medications

The following treatments are prohibited while in this study:

- No other investigational therapy should be given to patients. No anticancer agents other than the study treatment should be given to patients from ≤ 14 days prior to the first dose of BDTX-189 for standard chemotherapy and from ≤ 28 days or 5 half-lives, whichever is shorter, for investigational drugs until 30 days after the last dose of BDTX-189. If such agents are required for a patient, then the patient must first be withdrawn from the study.
- No routine pre-medications will be given during the DLT evaluation period (Day 1 to Day 21 in Cycle 1 [Part A]), however, based on emerging clinical experience in earlier cohorts/patients, prophylactic administration of medications may be permitted at the discretion of the Investigator.
- Concomitant treatment with any medication that is known to prolong the QT interval and/or cause Torsades de pointes is prohibited from 14 days before the start of treatment until the EOT visit (see [Appendix F](#)). After study enrollment, if a patient requires use of any of these medications, the patient must be removed from study.
- Drugs known to be strong CYP3A4 inhibitors or inducers are prohibited from ≤ 14 days before the start of treatment until the permanent discontinuation of treatment. Refer to [Appendix E](#) for a comprehensive list of agents in these categories. These agents include, but are not limited to:
 - CYP3A4 inhibitors: azole antifungals (ketoconazole, voriconazole and itraconazole), macrolide antibiotics (clarithromycin, erythromycin), HIV protease inhibitors (indinavir and ritonavir), cimetidine, aprepitant, nelfinavir, nefazodone, and double-strength grapefruit juice.
 - CYP3A4 inducers: phenytoin, barbiturates, and rifampicin.
- Herbal preparations/medications known to be potent inducers of CYP3A4 are not allowed from ≤ 14 days before the start of treatment until permanent discontinuation of treatment. These herbal medications include, but are not limited to, St. John's wort, kava, ephedra (ma huang), ginkgo biloba, dehydroepiandrosterone (DHEA), yohimbe, saw palmetto, and ginseng.

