Patients will be evaluated for response to treatment after 2 cycles of treatment. Response will be assessed at 6-week intervals (± 3 days) during the first 24 weeks (8 cycles) of study treatment. Thereafter, patients will be evaluated for response to treatment every 12 weeks (± 7 days), at the EOT visit (if not performed within the previous 4 weeks), and at the discretion of the Investigator. Patients with PD or unacceptable toxicity should be discontinued from the study; patients with SD or response to therapy will continue treatment. However, patients who are receiving clinical benefit in the opinion of the treating Investigator may be allowed to stay on study beyond initial radiological progression after consultation with the Medical Monitor if it is felt that it is in the patient's best interest. The assessments to be performed at this time are specified in [Appendix B](#). All target and non-target lesions documented at screening must be assessed. Please refer to Section [7](#) for further instructions on evaluating response (e.g., PD, SD).

The following assessments will be performed if abnormal at baseline or if clinically indicated:

- CT scan or MRI of chest, abdomen, and pelvis plus any other sites of known disease.
- CT scan head/MRI brain if history of CNS metastasis.

Investigators must ensure that images of all chest and abdomen CT/MRI scans for patients enrolled in Part B are available for transmission to the Sponsor for a future central reading by a BICR committee depending on preliminary efficacy results from Part A (see separate imaging charter).

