5.4. Follow-up Periods and Study Completion

5.4.1. End-of-Treatment Visit

The EOT visit will be performed as soon as possible (preferably within 3 days but no later than 14 days) after permanent discontinuation of the study treatment or when the Investigator decided with the patient to permanently discontinue the study treatment or when the Investigator became aware that the study treatment had been discontinued. The assessments of the EOT visit will then be performed instead of at the next planned visit. If the patient finishes treatment without having PD, tumor assessment/imaging must be performed at the time of treatment discontinuation unless it has been done within the past 4 weeks.

5.4.2. 30-day Safety Follow-up Visit

All patients will be followed during the off-treatment period until all treatment-related toxicity has resolved, or for at least 30 days (\pm 3 days) post-study drug discontinuation, or until the start

of another anti-cancer treatment, in which case this visit should occur before the start of subsequent therapy. Any concomitant medications received up to 30 days after the last dose of study medication should be recorded. For Part B and the Safety Expansion portion of Part A subsequent anticancer therapy will continue to be collected as outlined in Table 2 and Table 3.

Thirty-day Safety Follow-up visit assessments do not need to be repeated if a new anti-cancer therapy was initiated within 7 days of the EOT visit, unless further study drug was administered or there was a new abnormal test result when last assessed (including an abnormal test result which had worsened from previous). If the EOT visit is more than 30 days after the last dose of study treatment, the 30-Day Safety Follow-up visit is not required.

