5.4.3. Extended Follow-up Period (Safety Expansion and Part B)

For patients participating in Safety Expansion portion of Part A and all patients in Part B, additional follow-up for OS, PFS, and the first subsequent anti-cancer therapy after the 30-Day Safety Follow-up visit will be performed every 3 months (± 14 days) until 2 years after the first study drug dose if the patient has stopped treatment prior to PD based on RECIST Version 1.1 as assessed by the Investigator (see [Appendix B](#)) or another withdrawal criterion is met:

- Start of a new anti-cancer therapy.
- Lost to follow-up.
- Death.
- End of the whole study.

Follow-up information for OS may be obtained by phone.

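### Section 5.3.3 takes patients with unacceptable toxicity off the study, while 3.3 and Table 3 footnote s take them only off treatment; read literally, 5.3.3 can cost a Part B responder the confirming scan

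*Combined protocol and SAP*

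**What the plan says.** Two places end study participation:

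- 5.3.3 (Response Assessments): "Patients with PD or unacceptable toxicity should be discontinued from the study".
- 4.5.2 (Prohibited Concomitant Medications), on QT-prolonging drugs: "if a patient requires use of any of these medications, the patient must be removed from study".

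Other places stop treatment only and keep follow-up going:

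- 3.3 opens with "Patients will be discontinued from study treatment for any of the following reasons". Its list includes "Intolerable toxicity or abnormal laboratory values thought to be related to drug toxicity" and conditions needing an intervention that the protocol does not permit. Withdrawal of consent from the whole study is a separate item. For follow-up, 3.3 itself covers adverse events and laboratory values only: "After discontinuation from protocol treatment, patients must be followed for AEs for 30 days after their last dose of study drug".
- Table 3 footnote s (Part B): "Patients who discontinue treatment for reasons other than PD will undergo tumor assessment in accordance with the original schedule relative to C1D1".
- 5.4.1, for a patient who stops without progression: "tumor assessment/imaging must be performed at the time of treatment discontinuation unless it has been done within the past 4 weeks".
- 5.4.3 plans PFS and OS follow-up every 3 months "until 2 years after the first study drug dose if the patient has stopped treatment prior to PD". Table 3 footnote u gives the same interval and horizon.

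On the endpoint, 9.2 and 9.5.3 define the Part B primary analysis as confirmed ORR by central review, with the second assessment at least 4 weeks after the first. The response window in 9.2 closes at progression, death or new anti-cancer therapy, not at a treatment stop. The same section labels the intercurrent-event strategy while on treatment.

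**The concern.** A patient discontinued from the study has no further study scans; a patient discontinued from treatment does. Section 5.3.3 is where a site looks for response-assessment rules, and on this point it disagrees with the Part B schedule. The same patient could then be a confirmed responder at a site that follows footnote s and a non-responder at a site that follows 5.3.3. The observed ORR would depend partly on which section a site applied, and scans not taken cannot be recovered at analysis. Patients taken off study would also be censored early for PFS and, where a response had been confirmed, for DOR. Because the 5.3.3 sentence also names progression, a literal reading would end OS follow-up at progression, against footnote u.

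**Working it through.** **1. Who is exposed under a literal 5.3.3.** Scans are every 6 weeks (42 days) for 24 weeks, then every 12 weeks (84 days). Let the first-response scan be day 0 and the toxicity stop day d.

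- d up to 28: 5.4.1 waives the end-of-treatment scan, and a scan before day 28 would be too early to confirm. Under 5.3.3 nothing follows, so the response stays unconfirmed. Under footnote s the next scheduled scan can confirm it.
- d above 28: the end-of-treatment scan is mandatory and falls late enough to confirm, whichever section the site follows.

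The exposed part of the scan interval is about 28/42 = 67% in the first 24 weeks and 28/84 = 33% after that. It is approximate because scans have windows and 5.4.1 lets the end-of-treatment visit fall up to 14 days after the stop.

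**2. Reproducing the plan's error rates.** Inputs are the rules in 9.3.2. The method is exact binomial convolution over the stages.

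| Design | Stop if | Reject if | Null / target ORR | Type I error | Type II error |
|---|---|---|---|---|---|
| Cohorts 1, 2 | 0/15; ≤6/31 | ≥21/85 | 17.5% / 30% | 0.0459 | 0.1992 |
| Each Cohort 3/4 subgroup | 0/10 | ≥4/29 | 5% / 20% | 0.0468 | 0.1989 |
| Cohort 5 | ≤3/30 | ≥14/89 | 10% / 20% | 0.0478 | 0.1982 |

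All agree with Tables 12 to 15. Planned power is 1 − 0.1992 = 80.1%, 1 − 0.1989 = 80.1% and 1 − 0.1982 = 80.2%.

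**3. Effect of lost confirmations.** Let f be the share of true responders left unconfirmed. The documents give no value, so f is an assumption. The synopsis says the futility looks use response up to 6 weeks without confirmation, so the loss is applied at the final analysis only:

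Power(f) = Σₖ P(X = k and all futility looks passed) × P(Bin(k, 1 − f) ≥ r),

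where X is the total number of responders at the target ORR and r is 21, 4 or 14. As in Tables 12 to 15, a response is taken to be visible at whichever look falls due.

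| f | Cohorts 1, 2 | Each Cohort 3/4 subgroup | Cohort 5 |
|---|---|---|---|
| 0 | 80.1% | 80.1% | 80.2% |
| 2% | 78.2% | 79.1% | 78.6% |
| 5% | 74.8% | 77.5% | 75.9% |
| 10% | 67.2% | 74.3% | 70.1% |
| 15% | 57.3% | 70.7% | 62.9% |

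The same formula at the null ORR with f = 5% gives type I error of 0.030, 0.040 and 0.034, below the stated values in each design.

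**The case against.** The strongest reply is that the protocol uses study loosely to mean treatment. Section 5.3.3 sits under assessments during study treatment, its sentence goes on to contrast these patients with those who continue treatment, and 3.3 speaks of staying on study when it means staying on drug. Sections 5.4.1 to 5.4.3 and footnote s then set out off-treatment follow-up, and footnote s is specific to Part B. On that reading no scan is lost. This is probably what was intended, and it limits the point: harm needs a site to follow 5.3.3 over footnote s. It does not remove the contradiction, because 3.3 itself separates stopping treatment from leaving the study.

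A reader might infer more than the documents support:

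- That responders who stop for toxicity are generally lost. Only stops within about 4 weeks of the first-response scan are exposed. Those patients stay in the denominator as non-responders.
- That the 43.1% with Grade 3 or higher events in 1.1.7 shows how often this would happen. That figure is all-cause and pools all doses and schedules, including regimens above the MTD. It is not a discontinuation rate, and Table 8 handles many Grade 3 events by interruption or reduction.
- That the loss also acts at the futility looks. Thinning every stage gives 72%, 63% and 52% for Cohorts 1 and 2 at f = 5%, 10% and 15%, but those looks do not need confirmation, so this overstates the effect.
- That 3.3 orders continued scanning. It does not; footnote s does.

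The 4.5.2 limb is weaker. That section allows exceptions approved by the Medical Monitor. Its separate sentence on withdrawing patients who need other anti-cancer agents hardly matters for ORR, since new therapy closes the response window anyway.

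**Conclusion.** The contradiction is real and touches the Part B primary endpoint. Its effect is conditional: a site must apply 5.3.3 literally, and the responder must stop for toxicity within about 4 weeks of the first-response scan. The direction is known (ORR and power down, type I error not raised), but the size is not, because f cannot be obtained from the documents. Over the assumed range of 2% to 15%, power falls by about 2 to 23 percentage points in Cohorts 1 and 2, 1 to 9 in each Cohort 3/4 subgroup and 2 to 17 in Cohort 5. Given the narrow window, the true share may lie at or below the low end. The stated error rates in Tables 12 to 15 are correct and need no change. The while-on-treatment label in 9.2 adds to the ambiguity, because it could be read as excluding the off-treatment scans that footnote s requires and the 9.2 window admits.

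**What to change.** 1. In 5.3.3, and in the QT-drug sentence of 4.5.2, replace discontinuation or removal from the study with discontinuation from study treatment, to agree with 3.3. This concerns follow-up only; whether and when treatment stops stays as it is.
2. Cross-refer both places to Table 3 footnote s and 5.4.3. State that, in Part B, tumor assessments after a stop without progression continue on the schedule counted from C1D1 until progression, new anti-cancer therapy, death, withdrawal of consent, loss to follow-up or study end, with survival follow-up as in footnote u. Progression and new therapy must be on this list: footnote s ends scans at progression, 5.4.3 ends follow-up at new therapy, and 9.2 closes the response window at either.
3. In 9.2, reconcile the while-on-treatment label with the stated response window, and say whether a confirming scan taken after the last dose counts.

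The cost is wording in an amendment and a note to sites. The scans are already in the Part B schedule, and no sample size or decision rule changes.

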7. RESPONSE EVALUATIONS AND MEASUREMENTS

Response and progression will be evaluated in this study using RECIST Version 1.1 (see [Appendix B](#)). Lesions are either measurable or non-measurable according to the criteria. The term “evaluable” in reference to measurability will not be used, as it does not provide additional meaning or accuracy.

At screening, tumor assessments should encompass all areas of known predilection for metastases in the disease under evaluation and should additionally investigate areas that may be involved based on signs and symptoms of individual patients. These assessments should be performed no more than 28 days before the start of study treatment and, ideally, should be performed as close as possible to the start of study treatment. The methods of assessment used at screening should be used at each subsequent follow-up assessment.

Follow-up assessments should be performed every 6 weeks (± 3 days) after the start of BDTX-189 treatment for the first 8 cycles and every 12 weeks (± 7 days) thereafter. Any other sites at which new disease is suspected should also be appropriately imaged. If an unscheduled assessment is performed and the patient has not progressed, every attempt should be made to perform subsequent assessments at the scheduled visits while the patient remains on study treatment.

Categorization of objective tumor response assessment will be based on the RECIST v1.1 criteria for response: CR (complete response), PR (partial response), SD (stable disease), and PD (progressive disease).

If the Investigator is in doubt as to whether progression has occurred, particularly with response to non-target lesions (NTLs) or the appearance of a new lesion, it is advisable to continue treatment and reassess the patient’s status at the next scheduled assessment or sooner if clinically indicated.

To achieve “unequivocal progression” on the basis of non-target disease, there must be an overall level of substantial worsening in non-target disease such that, even in presence of SD or PR in target disease, the overall tumor burden has increased sufficiently to merit discontinuation of therapy. A modest increase in the size of one or more NTLs is usually not sufficient to qualify for unequivocal PD status.

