Progressive Disease (PD): At least a 20% increase in the sum of the diameters of target lesions, taking as reference the smallest (nadir) sum since the treatment started, or the appearance of one or more new lesions. Requires not only 20% increase, but absolute increase of a minimum of 5 mm over sum.

Evaluation of Non-Target Lesions

Complete Response (CR): Disappearance of all non-target lesions and normalization of tumor markers. All lymph nodes must be non-pathological in size (<10 mm short axis).

Non-CR/Non-PD: Persistence of one or more non-target lesions and/or persistence of tumor marker level above the normal limits.

Progressive Disease (PD): Appearance of one or more new lesions and/or unequivocal progression of existing non-target lesions. When the patient also has measurable disease, to achieve “unequivocal progression” on the basis of the non-target disease, there must be an overall level of substantial worsening in non-target disease such that, even in presence of SD or PR in the target disease, the overall tumor burden has increased sufficiently to merit discontinuation of therapy.

Evaluation of Best Overall Response

The best overall response is the best response recorded from the start of the treatment until disease progression/recurrence (taking as reference for PD the smallest measurements recorded since the treatment started). In general, the patient's best response assignment will depend on the achievement of both measurement and confirmation criteria.

Confirmation of response (by repeat scans after 4 weeks or as specified in the protocol) is required for trials in which response rate is the primary endpoint but is not required in randomized trials or trials with primary survival endpoints (i.e., where response is not a primary endpoint).

Note that a best overall response of SD requires an assessment of SD or better at the time of the first protocol-specified post-baseline tumor assessment (i.e., 42 days +/- 3 days after first dose) or later.

Target Lesions	Non-Target Lesions	New Lesions	Overall Response
CR	CR	NO	CR
CR	NON-CR/NON-PD	NO	PR
CR	NE	NO	PR
PR	NON-CR/NON-PD OR NE	NO	PR
SD	NON-CR/NON-PD OR NE	NO	SD
NOT ALL EVALUATED	NON-PD	NO	NE
PD	ANY	YES OR NO	PD
ANY	PD	YES OR NO	PD
ANY	ANY	YES	PD

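### Section 5.3.3 makes on-treatment chest, abdomen and pelvis imaging conditional while the Schedule requires it at every assessment; read region by region, 5.3.3 can let new lesions be missed or found late

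*Combined protocol and SAP*

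**What the plan says.** Section 5.3.3 (Response Assessments) sets the timing of response evaluation and then states: "The following assessments will be performed if abnormal at baseline or if clinically indicated". Two items follow. The first is "CT scan or MRI of chest, abdomen, and pelvis plus any other sites of known disease"; the second is head CT or brain MRI for patients with a history of CNS metastasis. The one imaging duty in 5.3.3 that carries no condition concerns known disease: "All target and non-target lesions documented at screening must be assessed".

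The Schedule of Assessments differs. Table 3 footnote s (Part B) reads "Tumor assessment (CT or MRI of chest, abdomen, and pelvis, plus other sites of known disease at baseline) will be performed every 6 weeks"; after eight cycles the interval lengthens to 12 weeks. Table 1 footnote w (Dose Escalation) and Table 2 footnote t (Safety Expansion) require the same coverage. None of the three attaches a condition.

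Appendix B counts this as progression on non-target assessment: "Appearance of one or more new lesions and/or unequivocal progression of existing non-target lesions". The baseline footnotes (Table 1 x, Table 2 v, Table 3 t) say "Baseline assessment must include CT or MRI imaging of the chest and abdomen, through the level of the adrenals", plus brain if clinically indicated and other sites of known disease. They do not name the pelvis. The 5.3.3 sentence on images to be held for central review names chest and abdomen only.

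**The concern.** RECIST detects progression in two ways: growth of known disease and the appearance of new disease. The second works only if regions that were clear at baseline are imaged again. As worded, 5.3.3 allows a site to skip such a region unless there is a clinical reason to scan it, although the Schedule tells the same site to scan it every time.

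If the scan is skipped, an asymptomatic new lesion there is not recorded at that visit and the patient keeps a rating of CR, PR or SD. The error runs in one direction for the patient affected, could differ between sites, and cannot be repaired later because the images do not exist. Part B plans about 80 centers, and its primary endpoint is confirmed ORR by blinded central review.

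**Working it through.** **1. The passages side by side**

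| Source | Coverage | Condition |
|---|---|---|
| Section 5.3.3, list | chest, abdomen, pelvis, known sites | abnormal baseline or clinical indication |
| Section 5.3.3, lesion sentence | lesions recorded at screening | none, but known lesions only |
| Table 1 w, Table 2 t, Table 3 s | chest, abdomen, pelvis, known sites | none |
| Baseline footnotes (Table 1 x, Table 2 v, Table 3 t) | chest, abdomen to adrenals, known sites | brain only if indicated |
| Section 5.3.3, images for central review | chest, abdomen | none |
| Section 7, follow-up | same methods as at screening; other sites | other sites only when new disease is suspected |

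**2. Does any text settle the conflict?** Section 4.4 says restaging imaging is as defined in the Schedule, citing Tables 1 and 3. Section 5.1 calls the Schedule complete, and Section 5.3 refers to it for visit detail. None of these says which text governs when they disagree. Section 5.3.3 also points to Appendix B, which defines methods and response categories but lists no regions to be scanned.

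**3. Does any text catch the missed lesion?** Section 7 covers suspected new disease, not asymptomatic disease. In the Appendix B response table, incomplete evaluation leads to NE only when target lesions are not all evaluated. Section 9.5.3 defines an adequate assessment as one rated CR, PR or SD and sets no minimum anatomical coverage. Section 10.3.3 has central review read the scans that are available.

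**4. Which endpoints can move?** PFS and DOR move whenever a new lesion in an unscanned region would have been the first sign of progression. DCR moves if that lesion was present at the assessment that set best response. Confirmed ORR moves only if target lesions have shrunk by at least 30%, the response is confirmed at least 4 weeks later, and the unseen lesion was there at or before confirmation. A lesion that appears after confirmation leaves ORR unchanged.

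**5. The plan's own figures.** An exact multi-stage binomial calculation reproduces every cumulative stopping probability in Tables 12 to 15. For Cohorts 1 and 2, for example, the Stage 1 stop under the null is (1 − 0.175)^15 = 0.0558. The probability of passing 0/15 and ≤6/31 and reaching at least 21/85 is 0.0459 at an ORR of 17.5% and 0.8008 at 30%.

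**6. How sensitive is the ORR rule?** The documents give no inflation figure. If observed ORR under the null were raised by an assumed number of percentage points, the probability of rejecting the null would be:

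| Cohort (rule) | +0 | +1 | +2 | +3 |
|---|---|---|---|---|
| 1 and 2 (≥21/85, null 17.5%) | 0.0459 | 0.0743 | 0.1130 | 0.1624 |
| Each subgroup of 3 and 4 (≥4/29, null 5%) | 0.0468 | 0.0801 | 0.1224 | 0.1725 |
| 5 (≥14/89, null 10%) | 0.0478 | 0.0886 | 0.1466 | 0.2208 |

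For scale, one patient in 29 is 1/29 = 3.4 points. The table shows only what an inflation would do; it is not evidence that one occurs.

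**The case against.** The strongest reply is that the protocol already places restaging imaging in the Schedule (Section 4.4), so a site following the visit tables would scan every time. The 5.3.3 item can also be read as one combined scan. Part B and the Safety Expansion require measurable disease, so that combined scan would be abnormal at baseline in most patients and the whole scan would be triggered. Section 7 adds that screening should cover areas of known predilection for metastases and that "The methods of assessment used at screening should be used at each subsequent follow-up assessment".

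Much of this stands. It makes the harmful reading less likely, and it rules out saying that lesions will be missed. It does not remove the conflict. The Section 4.4 pointer is not a precedence rule. Reading the item as one scan leaves the condition with almost nothing to do, so a regional reading is at least as natural. The pelvis is not named in the baseline footnotes and, unless it is a site of known disease, may never count as abnormal at baseline.

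Three stronger conclusions are tempting, and the documents support none of them.

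- A reader might infer that response and PFS are overstated. That needs sites to follow 5.3.3 rather than the Schedule, and to do so by region.
- A reader might assume that 10–20% of progressions are missed and conclude, from 1/(1 − d), that median PFS is inflated by 11–25% (1/0.90 = 1.11; 1/0.80 = 1.25). The documents give no such share, and the formula treats those events as never observed. Most would be found late, through target growth, an indicated scan or death, which is itself a PFS event. With exponential PFS and a delay of δ, the median ratio is 1 + ln(1 − d + d·e^(λδ))/ln 2, where λ = ln 2/median. Using medians of 4.2 and 9.6 months (two of the comparator figures in Sections 1.1.2 and 1.1.3) and the same assumed d, a 6-week delay gives about 1.5–7% and a 12-week delay about 3–16%. Even these figures assume that every site follows the regional reading.
- A reader might count every patient with some target shrinkage and an unseen lesion as a false responder. The 30% threshold and the confirmation rule exclude that.

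**Conclusion.** The contradiction is real, and it concerns how progression and response are ascertained in all three parts. Where a site applies 5.3.3 region by region, an asymptomatic new lesion can be missed or found late. In that patient the effect can only favour DOR, DCR and PFS; it favours ORR only in the narrower case set out above. The secondary endpoints are therefore more exposed than the primary one.

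The size cannot be estimated. The documents give neither the share of progressions that first appear in a region clear at baseline nor any indication of how sites would read 5.3.3. The type I error table and the PFS range rest on assumed inputs and show sensitivity only. Planned sample size, alpha and power are unaffected. This is an internal inconsistency rather than a deliberate design choice. It is worth correcting because the bias would run one way and skipped scans cannot be recovered.

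**What to change.** In Section 5.3.3, remove the condition for chest, abdomen and pelvis. State that these regions, and other sites of known disease, are imaged at every scheduled assessment as set out in the Schedule footnote for the relevant part: Table 1 w, Table 2 t or Table 3 s. Keep the condition for head CT or brain MRI only. Refer to the footnotes rather than pasting footnote s into 5.3.3: footnote s carries a rule on assessments after treatment discontinuation that footnotes w and t do not have, and 5.3.3 also covers Part A.

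In the same edit, reconcile two other texts with the scheduled chest, abdomen and pelvis coverage: the baseline footnotes (Table 1 x, Table 2 v, Table 3 t), which stop at the adrenals unless disease is known elsewhere, and the 5.3.3 sentence on images for central review, which omits the pelvis.

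The cost is a short wording amendment. It adds no on-treatment scan, because the Schedule already requires them, and changes no sample size or decision rule. If the baseline footnotes are extended to the pelvis, that region would be added at screening for patients in whom it is not already imaged.
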